# 1 Schematic of Study Design

# 2 Background Information and Rationale

### 2.1 Background Information

**Our adult bodies harbor** ~10 times more microbial cells than human cells. Collectively they are known as the human microbiome. A significant number of these microbes are difficult to grow in culture leading to inherent biases in the use of culture based methods to describe it. Our microbiome carries out many metabolic reactions not encoded for in the human genome and are necessary for our health. The NIH funded Human Microbiome Project (HMP) was developed to "to understand the microbial components of the human genetic and metabolic landscape and how they contribute to normal physiology and predisposition to disease" (1). The HMP's focus is on characterizing the microbiome of the gastrointestinal tract, the oropharynx, the anterior nares, the vagina and the skin in young healthy adults.

Staphylococcus aureus (SA) is a part of the human microbiome and an important cause of both community and hospital acquired infections. Methicillin-resistant *S. aureus* (MRSA) is a type of *S. aureus* which is resistant to penicillin-like antibiotics, but susceptible to other antibiotics. *S. aureus* which are not methicillin resistant is referred to as methicillin-susceptible *S. aureus* (MSSA). *S. aureus* is a normal part of the human microbiome. Colonization is frequently prolonged (6) and patients are at risk for infection when the opportunity (e.g. central line or surgery) occurs. Patients with *S. aureus* colonization serve as the source of transmission to others thus preventing transmission decreases infections by reducing the number of patients who serve as a source of transmission. Efforts to decolonize patients with *S. aureus* colonization have not been successful in the long-term (7).

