### 2.2 Rationale

Given the role of our normal flora in serving as a barrier to colonization with more pathogenic organisms (aka colonization pressure), decolonization regimens may have unintended negative consequences. For example, preliminary 16S rRNA data suggest that Gram-negative bacilli from the orders Enterobacteriales and Pseudomonadales are present as a component of the human microbiome of the anterior nares. Decolonization with intranasal mupirocin, a Gram-positive antimicrobial agent, may increase this Gram-negative colonization and consequently increase the likelihood of infections due to these pathogens. The recent Cochrane Review of Mupirocin ointment for Preventing S. aureus infections in nasal carriers concluded that the use of mupirocin led to a relative increase in infections due to bacteria other than S. aureus (Analysis 6.1: RR 1.4 95%CI 1.1-1.7) and that infections due to Gram-negative bacilli were increased but not statistically significant (Analysis 6.3: RR 1.7 95%CI 0.8-3.5)(7). Although suggestive, these analyses are limited in scope because few of the mupirocin clinical trials have reported overall infections. Many, including the recent NEJM paper, have just focused on S. aureus infections (13). Furthermore these trials have not looked at the impact of mupirocin on colonization with other organisms. If mupirocin promotes colonization with Gram-negative bacilli, this is an important adverse event given that colonization with Gram-negative bacilli increases the risk of Gram-negative bacilli infection in hospitalized patients (17-19) and the increasing antibiotic resistance in the Enterobacteriaceae, Pseudomonas and Acinetobacter over the past decade (20). Our short term goal is to determine if these increasingly used decolonization regimens, targeted at controlling MRSA in particular, may result in a secondary negative effect of promoting colonization with pathogenic Gram-negative bacilli. This could be an unintended consequence of healthcare policies which are indirectly promoting the use of these decolonization regimens and would have an impact of the use of mupirocin for infection control purposes. The long term goal of this research is to use the information gained to develop new ways to manipulate the human microbiome to reduce the risk of S. aureus infections with minimized negative consequences.

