### 5.2 Inclusion Criteria

- Adults living independently in the Baltimore area
- Willing and able to provide anterior nares, throat, skin, and perirectal specimens over up to an 18 week time period.
- Willing and able to administer intranasal mupirocin and topical chlorhexidine over a five day period.
- Capable of understanding and complying with the entire study protocol.
- Provided signed and dated informed consent.
- *S. aureus* colonization on at least one of the enrollment cultures (after informed consent)

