### 8.2 Laboratory Evaluations

During each study visit a specimen is obtained by trained research personnel from each of the following sites: anterior nares, posterior pharynx, skin over the femoral vein, skin over the subclavian vein, and perirectal skin. These specimens are tested for MRSA, MSSA and gramnegative bacilli in the Research Microbiology Laboratory and are also analyzed for the presence of all bacteria using metagenomics techniques.

In addition, a blood sample taken at the enrollment visit will be initially processed in the GCRC and transported to the Research Microbiology Lab for storage until immunologic and genotypic tests are performed.

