### **11 Statistical Plan**

#### 11.1 Analysis Plan for Microbial Community Profiling

In this project, we will utilize model-based statistical methods to study the dynamics and composition of the microbial communities present in the anterior nares, posterior pharynx and three skin sites in two populations (Protocol HP-51033 Nursing home dwelling MRSA Colonized Adults and this protocol) with and without current exposure to the healthcare environment, and before and after decolonization using treatment with topical chlorhexidine and intranasal mupirocin. These analyses will be performed in association with the various metadata collected and will be critical to be able to answer the various questions associated with our project, which include:

Aim 1:

Over time within individuals and at the nose and throat, and skin sites- what are the microbial communities present, their relative/absolute abundance? Are there differences between individuals at the nose and throat by living environment (community-dwelling vs. nursing home dwelling)? Aim 2:

What are the changes, within individuals, in the microbiome associated with decolonization over time at the nose, throat, and skin sites in term or composition and relative/absolute abundance?

What are the changes in the microbiome of each individual from the baseline to after decolonization at the nose, throat, and skin sites, in relation to decolonization and living environment (community-dwelling vs. nursing home dwelling)?

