The assignment of 16S sequencing reads to OTUs will be performed using OTUPicker (23, 24), the Ribosomal Database Project Bayesian classifier (25) and Hidden Markov Chain modelsbased algorithms developed at UMD-IGS by Drs. [name] and [name] to classify a subgroup of OTUs to the species level (for details about the speciation analysis, see (26)). OTU classification data for each sample will then be utilized for model-based comparative analyses of community structure. Model-based approaches directly use the observed raw data, and minimize the loss of information by eliminating the data reduction steps associated with distance-based methods (used in OTU classification tools such as DOTUR (24), UNIFRAC (25) and SONS (23)). The Bayesian and likelihood statistical frameworks used in these approaches provide a probabilistic measure of confidence in the results and facilitate comparisons between the different models and methods through the use of model-selection strategies such as Bayes factors, Akaike's information criterion, Bayesian information criterion and decision theory, and hypothesis-testing approaches. Moreover, model-based approaches allow for incorporation of metadata along with data used to infer the group membership of OTUs that comprise the microbial communities under study. This information is then used to cluster these communities. Model-based approaches also provide a classification tool to assign newly sampled individuals to pre-existing groups that result from clustering approaches that take both metadata and microbial community composition into account.

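### Aim 2's whole-community results do not separate the intended loss of S. aureus from change in the other bacteria; Section 11.1 should add an analysis with S. aureus removed

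*Protocol*

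**What the plan says.** The Aim 2 outcome is set out in Protocol Section 11.1: "What are the changes, within individuals, in the microbiome associated with decolonization over time at the nose, throat, and skin sites", to be described "in term or composition and relative/absolute abundance". A second Aim 2 question relates change from baseline to living environment, using a separate nursing-home cohort.

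S. aureus is inside the community being measured. Section 2.1 says it "is a part of the human microbiome and an important cause of both community and hospital acquired infections". Under Section 8.2 the specimens "are also analyzed for the presence of all bacteria using metagenomics techniques". Section 11.1 continues: "OTU classification data for each sample will then be utilized for model-based comparative analyses of community structure". On group membership of OTUs it adds: "This information is then used to cluster these communities". Nothing in 11.1 sets S. aureus apart.

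Participants are selected on the same organism. Section 5.2 requires S. aureus on one or more enrollment cultures, and Section 5.4 withdraws anyone whose visit 1 specimens are all negative. Section 2.3 expects the regimen to clear S. aureus in the short term.

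The motivating question is about other organisms. Section 2.2 asks whether these regimens "may result in a secondary negative effect of promoting colonization with pathogenic Gram-negative bacilli".

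**The concern.** The organism that the treatment targets is a component of the outcome used to look for effects on everything else. A regimen that removed S. aureus and left all other bacteria alone would still register as a change in community structure, and could move a sample from one cluster to another. It would also raise the relative abundance of every untouched taxon, Gram-negative bacilli included, with no real growth.

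A community-level change could then be read as collateral disturbance when it is only the intended effect. The comparison by living environment is exposed in the same way: two cohorts that start with different amounts of S. aureus can differ in change for that reason alone.

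**Working it through.** **Plan's own figures.** The plan gives no effect size, baseline S. aureus share or power basis for Aim 2. Its only derived figure is the sample size in Section 11.3: 250 × 1/5 − 10 = 40. This reproduces, and the present point does not affect it.

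**Assumed inputs.** Baseline S. aureus read share p is taken from 1% to 50%. All other taxa keep their absolute counts.

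**Shift from S. aureus loss alone.** Let r be the composition of the other bacteria. Before treatment the sample is (p, (1−p)r). After complete loss it is (0, r). Bray-Curtis dissimilarity is 1 minus the sum of the smaller shares, so 1 − (1−p) = p. With 90% loss it is p − 0.1p/(1−0.9p). After complete loss, an untouched taxon rises in relative abundance by 1/(1−p). With S. aureus removed and the rest rescaled, both samples equal r and the shift is 0.

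| p | Shift, complete loss | Shift, 90% loss | Fold rise of untouched taxon, complete loss | Shift with S. aureus removed |
|---|---|---|---|---|
| 1% | 0.010 | 0.009 | 1.01 | 0 |
| 5% | 0.050 | 0.045 | 1.05 | 0 |
| 10% | 0.100 | 0.089 | 1.11 | 0 |
| 30% | 0.300 | 0.259 | 1.43 | 0 |
| 50% | 0.500 | 0.409 | 2.00 | 0 |

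**A real collateral change can be hidden.** Let a Gram-negative taxon holding 3% of the remainder truly double, with complete S. aureus loss. At p = 10%, 30% and 50% the whole-community shift is still 0.10, 0.30 and 0.50, as with no doubling, because every other taxon's share rises anyway. With S. aureus removed the shift is 0.06/1.03 − 0.03 = 0.028 in all three cases.

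**Absolute scale.** With p as the share of total load, Bray-Curtis on counts is p/(2−p): 0.10/1.90 = 0.053 at 10% and 0.30/1.70 = 0.176 at 30%. The false rise of other taxa disappears, but the loss still counts as community change.

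**Model-based version.** Section 11.1 prefers models to distances and names the Bayesian information criterion (BIC). Assume 1,000 reads per sample, multinomial sampling, S. aureus plus six other taxa, and complete loss. The likelihood-ratio statistic for two communities against one is 2 × 1,000 × [p ln 2 + (1−p) ln((1−p)/(1−p/2)) − ln(1−p/2)]. This gives 13.9, 70.6, 143.9 and 469.1 at p = 1%, 5%, 10% and 30%; the six other taxa relative to one another contribute 0. The BIC penalty is 6 × ln(2,000) = 45.6. So BIC declares two communities from S. aureus loss alone at 5% and above, and not at 1%. At p = 10%, the Gram-negative doubling above contributes about 9 of a total of about 153.

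**Comparison by living environment.** If one cohort starts at 10% and the other at 30%, complete loss with no collateral effect gives shifts of 0.10 and 0.30, a difference of 0.20.

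**The case against.** The protocol already has routes that tell the two apart:
- Section 11.3 describes comparing many OTUs before and after decolonization, so S. aureus loss and change in other taxa fall on different OTUs.
- Aim 2 names absolute as well as relative abundance.
- Section 8.2 cultures MRSA, MSSA and Gram-negative bacilli at each visit, and Section 11.2 analyses them apart from the community profile.

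Whole-community change is also a legitimate objective under Section 3, and S. aureus belongs in it. Bray-Curtis is not the planned method. An extra run without one taxon could sit in a statistical analysis plan that is not shown.

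Much of this stands. A reader might infer that S. aureus loss cannot be told from collateral damage; the routes above show otherwise. A reader might infer that a positive community result is close to guaranteed. That is unsupported, because carriage is needed at only one of five sites, no read share is given, and at 1% the effect is negligible. A reader might also expect people who clear S. aureus to show more microbiome change than those who do not, but Section 3 compares those groups on antibody level and genotype only.

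What remains is narrower. The cultures say nothing about bacteria outside the groups cultured, and the Gram-negative acquisition tests in 11.2 compare cohorts rather than before with after. Absolute abundance removes the false rise in other taxa but leaves S. aureus in the community measure. The likelihood calculation shows that the preference for models does not remove the problem. The mismatch between the question in 2.2 and the outcome in 11.1 is in the protocol itself.

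**Conclusion.** The point holds in limited form. Aim 2's community-level results and relative abundances, as written, do not separate the intended S. aureus loss from change in the other bacteria. The protocol's other analyses separate them in part.

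The artefact equals the baseline S. aureus share on the Bray-Curtis scale if loss is complete: about 0.01 at 1%, 0.10 at 10% and 0.30 at 30%, and near zero at sites with little S. aureus. These shares are assumptions. Bray-Curtis is only an illustrative index. The likelihood figures further assume 1,000 reads and multinomial sampling; a model allowing for extra variation between samples would give smaller statistics.

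The whole-community analysis is not wrong as a description of what the regimen does. It is a weak guide, used alone, to what happens to the other bacteria. This is a worthwhile, cheap improvement and not a defect that invalidates the study.

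**What to change.** Keep the whole-community analysis for Aim 2. Add to Section 11.1 that the collateral-effect question is also analysed on the non-S. aureus community: remove the S. aureus OTUs, rescale the remaining reads, then repeat the clustering, the pre/post comparison and the comparison by living environment. Report the change in S. aureus itself beside both results. If a statistical analysis plan already specifies this, a cross-reference is enough.

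Section 11.1 promises species-level calls for only a subgroup of OTUs. Where S. aureus cannot be assigned, removing all staphylococcal OTUs should be a labelled sensitivity analysis only. It also deletes non-target staphylococci, which the regimen may affect, given the activity described in Section 2.1, and so can understate collateral change.

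The cost is one extra run of the same models on data already held, with no new specimens or participants. The downsides are fewer usable reads at sites dominated by S. aureus and dependence on the quality of the species calls.

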### 11.2 Analysis Plan for Microbiologic Data

The goals of the microbiological analysis are two-fold. The first goal is descriptive to document the effectiveness of the regimen in reducing colonization with MRSA, MSSA and pathogenic Gram-negative bacilli at the body sites sampled. The second goal will compare the effectiveness of the regimen in the two different populations. We will assess whether there are differences in acquisition of GNB and antibiotic resistant GNB between community-dwelling and nursing home-dwelling adults. We will compare weeks to MRSA or MSSA re-colonization in each body site by living environment using survival curves and the Wilcoxon log rank test. We will compare whether there are differences in the acquisition (among those negative at baseline) of specific GNB and resistant GNB between community-dwelling and nursing MRSA or MSSA-colonized adults using chi-square tests or Fisher's exact test as appropriate.

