There may be adverse events that are not yet known. For example, we are studying whether mupirocin leads to an increase in Gram-negative colonization in the anterior nares and throat which might lead to an increased risk of Gram-negative infections. To date, there is evidence that mupirocin leads to an increase in the relative risk of infections due to organisms other than *S. aureus* including Gram-negative bacilli (7); however, this was in surgical and dialysis patients, a group at increased risk for infections in genera and was not associated with an absolute risk of infectionl. In general, Gram-negative bacilli are opportunistic pathogens. They colonize frequently, but infrequently cause infection. To minimize the risk of infection, we are excluding older adults who would be at increased risk of infection (e.g. surgical and dialysis patients, those with recent hospitalizations, history of urinary tract infections).

There is no alternative treatment or procedure to participating in this study, but individuals have the right to decline participation in this research without any risk.

There are no direct benefits to study participants. Participants will receive a regimen that will eradicate *S. aureus* colonization in the short term. Although *S. aureus* colonization contributes to the risk of *S. aureus* infection, the absolute risk of *S. aureus* infection is small enough that this is not believed to be a direct benefit. This study will contribute knowledge about the human microbiome. *S. aureus* and other opportunistic pathogens are members of this

January 9, 2020

microbiome. When the opportunity arises (e.g. a person has surgery or a central venous catheter), these bacteria can cause an infection particularly in hospitalized patients. Understanding the human microbiome in *S. aureus* colonized participants can help us develop new ways to prevent *S. aureus* infections.

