# 4 Study Design

### 4.1 Primary Study Endpoints/Secondary Endpoints

When examining the baseline microbiome as a whole, characterizing the distribution of 16S bacterial sequences present is the 'endpoint'. The study will also look at changes to the baseline microbiome following decolonization regimens.

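### Section 11.2 specifies no within-participant before/after comparison of culture-detected Gram-negative bacilli, and its one named Gram-negative test compares two populations that are both decolonized

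*Protocol*

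**What the plan says.** Section 2.2 gives as the short-term goal finding out whether decolonization regimens "may result in a secondary negative effect of promoting colonization with pathogenic Gram-negative bacilli". Section 2.3 repeats this to explain possible unknown harm: "we are studying whether mupirocin leads to an increase in Gram-negative colonization in the anterior nares and throat".

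Section 11.2 sets two goals for the culture data. The first is within the population: "The first goal is descriptive to document the effectiveness of the regimen in reducing colonization with MRSA, MSSA and pathogenic Gram-negative bacilli". The second compares the two populations. Its Gram-negative part tests, by chi-square or Fisher's exact test, "differences in the acquisition (among those negative at baseline) of specific GNB and resistant GNB between community-dwelling and nursing MRSA or MSSA-colonized adults".

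Section 11.1 describes those populations, community-dwelling adults here and nursing-home adults in a companion protocol, as studied "before and after decolonization using treatment with topical chlorhexidine and intranasal mupirocin". Its Aim 2 asks: "What are the changes, within individuals, in the microbiome associated with decolonization over time at the nose, throat, and skin sites". It refers to both relative and absolute abundance and lists hypothesis testing among its tools. Section 11.3 adds that OTUs are compared before and after decolonization, with participants as their own controls.

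Section 8.1 schedules three specimen sets before the regimen (Day 0, Weeks 4 and 8) and five after it up to Week 16 (Weeks 9, 10, 11, 12 and 16). Under Section 8.2, specimens from each visit are cultured for Gram-negative bacilli as well as sequenced.

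**The concern.** The question is about an increase caused by the regimen. The culture analysis describes a reduction and then tests a difference between two treated groups. A rise shared by both groups leaves that difference at zero.

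The acquisition measure has a second weakness. A participant who is negative at baseline can only stay negative or become positive. Ordinary fluctuation in detection therefore produces some acquisition with no regimen effect, and Section 11.2 gives no background rate to set beside it.

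Followed as written, the study could report a sizeable acquisition percentage that a reader takes as harm, or a non-significant between-population test that a reader takes as reassurance. Neither reading would be justified. The pre-treatment cultures that could supply the reference are already collected.

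**Working it through.** **1. Question against analysis.**

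| Section | What it addresses |
|---|---|
| 2.2, 2.3 | Does the regimen increase Gram-negative colonization (nares and throat in 2.3)? |
| 11.2, first goal | Description of the regimen reducing Gram-negatives |
| 11.2, second goal | Acquisition, community versus nursing home, both decolonized |
| 11.1 Aim 2, 11.3 | Pre/post 16S change over all taxa; no Gram-negative contrast named |

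No row is a before/after comparison of Gram-negative culture results within participants.

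**2. The plan's own figure.** Section 11.3 enrols 250, assumes one in five colonized with *S. aureus*, and loses 10: 250 × 1/5 − 10 = 40. The stated final size reproduces. (Section 4.2 names a goal of 50; 40 is used here.) The protocol states no Gram-negative rate, so all rates below are assumptions.

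**3. What the between-population test can show.** Assume 40 per group (the nursing-home number is not given), the same acquisition risk in both groups, and two-sided 5% Fisher's exact test, with rejection probability summed over all tables:

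| Common risk | 5% | 20% | 30% | 50% |
|---|---|---|---|---|
| Rejection | 0.4% | 2.8% | 2.8% | 3.3% |

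The rate stays below 5% however large the shared increase.

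**4. Acquisition with no regimen effect.** Assume constant detection probability p per visit, one negative baseline culture, and acquisition counted as any positive over five later cultures.

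- Independent visits: 1 − (1 − p)^5. For p = 0.05, 0.10, 0.20: 23%, 41%, 67%.
- Correlated visits (beta-binomial, within-person correlation ρ, a = p(1 − ρ)/ρ, b = (1 − p)(1 − ρ)/ρ): 1 − ∏(b + j)/(a + b + j), j = 1 to 5.
 - p = 0.10, ρ = 0.2 (a = 0.4, b = 3.6): 1 − (4.6/5)(5.6/6)(6.6/7)(7.6/8)(8.6/9) = 27%.
 - p = 0.10, ρ = 0.4 (a = 0.15, b = 1.35): 1 − (2.35/2.5)(3.35/3.5)(4.35/4.5)(5.35/5.5)(6.35/6.5) = 17%.
- Over ρ = 0.4 to independence, the range is 9% to 23% at p = 0.05 and 32% to 67% at p = 0.20.
- If baseline-negative means three negative cultures, the p = 0.10 figures at ρ = 0.2 and 0.4 fall to 21% and 12%. They do not vanish.

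**5. A matched reference removes this.** Use one negative culture followed by two cultures 4 and 8 weeks later. Before treatment that is Day 0, then Weeks 4 and 8. Across treatment it is Week 8, then Weeks 12 and 16. At p = 0.10 and no effect, both sides expect 1 − 0.9² = 19% (independent), 1 − (4.6/5)(5.6/6) = 14% (ρ = 0.2) or 1 − (2.35/2.5)(3.35/3.5) = 10% (ρ = 0.4). The expected difference is zero in each case.

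**6. Relative 16S share.** Suppose reads are 80% Gram-positive, 5% the Gram-negatives of interest and 15% other, and only the Gram-positives fall, f-fold. The Gram-negative share changes by [5/(5 + 15 + 80/f)]/0.05, which is 2.8-fold at f = 5 and 3.6-fold at f = 10, with Gram-negative numbers unchanged. A Gram-negative to Gram-positive ratio would rise 5- to 10-fold, so a log-ratio on that reference does not cure the problem.

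**7. What 40 participants can detect.** Exact two-sided 5% McNemar test, one pre and one post status per participant, 40 pairs:

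| Lose carriage | Gain 20% | Gain 25% | Gain 30% | Gain 35% |
|---|---|---|---|---|
| 2.5% | 0.57 | 0.77 | 0.89 | 0.96 |
| 5% | 0.36 | 0.57 | 0.74 | 0.86 |
| 10% | 0.13 | 0.27 | 0.44 | 0.61 |

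With 2.5% to 5% losing carriage, reasonable power needs a net increase of about 25 to 30 percentage points. With 10% losing it, power at a net 25 points is only 0.61.

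**The case against.** The strongest reply is that the question is tested, by sequencing. Section 2.2 motivates it with 16S data on Gram-negative orders. Section 11.1 plans within-individual change with hypothesis testing, and Section 11.3 compares OTUs before and after. This stands against the stronger reading a reader might form, that the study has no test bearing on Gram-negative change. It does not repair Section 11.2: no Gram-negative taxon, contrast or direction is singled out in Section 11.1, and the culture data keep the opposite wording.

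A reader might also infer that the 16S analysis rests on relative share alone. Section 11.1 names absolute abundance too, so the share artefact is a caution for the relative measure only, and its inputs are assumed.

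Nor does the protocol say that acquisition means any positive over five visits, or that baseline means one culture. Documenting effectiveness would presumably use some pre-treatment results. The percentages in step 4 are illustrations, and 41% needs independent visits, which is unlikely for colonization.

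Finally, model details and definitions may properly sit in an SAP that is not shown. That is fair. The mismatch between the question in Sections 2.2 and 2.3 and the goals fixed in Section 11.2 lies within this document.

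**Conclusion.** The point holds for the culture analysis. Section 11.2 specifies no within-participant comparison of Gram-negative positivity before and after the regimen. Its descriptive goal is worded against the stated question, and its one named Gram-negative test cannot detect an effect common to both populations. That last conclusion needs no assumed rate, only that both groups are decolonized, as Section 11.1 says.

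Acquisition as planned has no reference. How far that misleads depends on assumptions: 17% to 41% with no effect at 10% detection per visit, and 9% to 67% over the wider range examined.

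The documents do not support saying that Gram-negative change goes untested, since 16S covers it generically. They do not support saying that no untreated reference is available, since three pre-treatment culture sets exist; there is simply no concurrent untreated group. They also give no ground for replacing the 16S endpoint in Section 4.1.

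**What to change.** Leave the 16S endpoint in Section 4.1 as it is, and amend Section 11.2:

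1. For Gram-negative bacilli, write of the regimen changing colonization instead of reducing it.
2. Add a within-participant, visit-level analysis (GEE or mixed logistic) of culture-detected pathogenic Gram-negatives in nares and throat, Weeks 9 to 16 against Day 0, Week 4 and Week 8. Include all participants whatever their baseline status, and report the odds ratio with its 95% confidence interval.
3. Report acquisition beside a pre-treatment reference with the same rule and spacing, for example negative at Day 0 then positive at Week 4 or 8, against negative at Week 8 then positive at Week 12 or 16. Do not take the reference from participants required to be negative at all three pre-treatment cultures: their pre-treatment rate is zero by construction.
4. State that a rise in relative 16S Gram-negative share is not read as an increase in Gram-negatives unless absolute abundance or culture agrees.
5. Keep the between-population test as secondary.

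The cost is wording and a little more analysis; the cultures are already scheduled. The matched rule in item 3 omits Weeks 9 to 11, so an early, short-lived rise would have to be seen in item 2. Precision at 40 participants is limited, so the estimate and interval matter more than the p-value. A before/after comparison cannot exclude time trends, and the protocol should say so.
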